5.0 Inclusion and Exclusion Criteria/ Study Population

The participants in this study include persons with Alzheimer's disease (PWD) and their caregivers (CG).

- *Inclusion Criteria:*

- *Persons with Alzheimer's Disease or Mild Cognitive Impairment (we anticipate cognitive impairment within this group)*
 - *18 years old or older*
 - *Diagnosis of Alzheimer's Disease, suspected Alzheimer's disease or Mild Cognitive Impairment with (FAST score ≤4)*
 - *Able to read and speak English (intervention in English)*
- *Caregivers (CG)*
 - *≥ 18 years old*
 - *Non-paid (eliminates professional caregivers)*
 - *Provides care to someone living with Alzheimer's, suspected Alzheimer's disease or Mild Cognitive Impairment. Able to read and speak English (written materials in English)*
 - *No diagnosis of cognitive impairment*

Exclusion Criteria

- Inability or unwillingness to provide informed consent

Inclusion of a diverse population

Families with loved-ones with Alzheimer's Disease from all racial and ethnic backgrounds will be approached and invited to participate as research participants.

Statement on the non-inclusion of children

Alzheimer's disease is typically observed in older adults and not in children. Hence children are excluded from the study population.

6.0 Number of Subjects

Total of up to 60 participants (30 dyads) up to 30 persons with Alzheimer's or Mild Cognitive Impairment and 30 caregivers. Dyad members may participate individually if a caregiver is unavailable or PLWD chooses to not participate.

7.0 Setting

All aspects of this study will take place using virtual MUSC communication platforms means such as telephone, email or a meeting platform such as MS Teams. Initial study procedures (consent, basic demographic questionnaire and baseline measures) and subsequent visit measures will be completed remotely using REDCap survey. Post-intervention interviews will be conducted virtually. Participants will be able to participate in this study in the comfort and privacy of a setting of their own choosing.

8.0 Recruitment Methods

- **Person with Alzheimer's/Caregiver Recruitment**-Providers at MUSC Memory Disorder Clinic and/or MUSC Geriatric Clinic will identify potential participants dyads and ask permission from the patient/caregiver for the PI or program coordinator (PC) to contact the caregiver for screening. Once permission is granted, the PI, or PC will contact the caregiver and assess for eligibility and enrollment.
- Study participants from [name] ([name]: R01 and Supplement) and [name] (Multi-site R01) study population (those who agreed to be contacted for future studies) will be contacted.

- Study flyers will also be placed in clinic and public areas throughout the Medical University of South Carolina Enterprise. The flyers will include the PI/PC contact information; interested participants who call the PI/PC will be screened for eligibility.
- Electronic flyers, advertisements, and study information will be posted on social media channels (e.g., Facebook), on Research Match, and will be sent to professional and community-based organizations focused on care of people with Alzheimer's Disease to disseminate among their clients.
- Flyers will also be shared with local respite care centers offering early memory loss programs to share with potentially interested participants
- Families with loved ones that have been recently diagnosed with Alzheimer's Disease and are seen in the clinics of research team members who are MUSC clinicians will be approached and given a study flyer.
- The researchers will submit a BMIC honest broker Research Data Request to obtain a recruitment report of MUSC patients who potentially meet the study's eligibility criteria (ICD diagnosis of Alzheimer's Disease). The researchers will not cold-contact any patients who have chosen to opt-out of receiving contact about research and/or that have reached the maximum contact attempts at the time of recruitment. Researchers will use a Cold Calling telephone script to approach patients and follow MUSC policies and procedures for Cold Contact.

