Sample size considerations: The purpose of this study is to establish feasibility, acceptability, and practicability of implementing the SUPPORT-D intervention, therefore a sample size calculation was not performed. Sample size for Phase II was determined for pragmatic reasons including time to deliver intervention, and availability of mobile devices for intervention delivery, The PI and PC plan to recruit participants over a three-month period using methods described within section 8 of this protocol. To ensure a consistent workload of the PI and interventionist we anticipate recruiting 1-2 dyads weekly during the recruitment period for up to 30 PWD/CG dyads.

Compensation: Reimbursement for dyads will be \$100 provided in \$25 increments over four time periods (enrollment/baseline data collection, study visit 1, study visit 2, and post intervention visit) with dyads in key informant interviews receiving an additional \$25.

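### The records query is limited to an Alzheimer's disease ICD code, although MCI and suspected Alzheimer's disease are also eligible, so this channel under-represents part of the admitted population

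*Combined protocol and SAP*

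**What the plan says.** Section 5.0 (Inclusion and Exclusion Criteria) lists three qualifying diagnoses for the person with cognitive impairment: Alzheimer's disease, suspected Alzheimer's disease, and "Mild Cognitive Impairment with (FAST score ≤4". Section 6.0 (Number of Subjects) again counts people with Alzheimer's "or Mild Cognitive Impairment and 30 caregivers".

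Section 8.0 (Recruitment Methods) sets out seven routes. One is a records search through an honest broker, which is to return patients at the institution who may satisfy the "eligibility criteria (ICD diagnosis of Alzheimer", so the code for Alzheimer's disease is the only diagnosis named. Patients on that report may be cold-contacted, subject to opt-outs and contact limits. A second route, in which team clinicians hand flyers to families in their own clinics, also names only a recent Alzheimer's disease diagnosis. The other five state no diagnosis restriction. They include clinic referral ("Providers at MUSC Memory Disorder Clinic and/or MUSC Geriatric Clinic will identify potential participants dyads") and flyers, for which "interested participants who call the PI/PC will be screened for eligibility".

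Table 2 in section 10.0 lists recruitment rates, percent eligible and consent among the feasibility measures. The Statistical Analysis Plan paragraph of the same section gives a 95% confidence interval for the proportion agreeing among people approached. Neither is split by diagnosis or by recruitment route. For people who fail screening, section 12.0 records gender, age, race and the reason for exclusion.

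**The concern.** The report is presented as finding potentially eligible patients, but its criterion is narrower than the eligibility criteria. A patient with an MCI record and no Alzheimer's disease code is eligible on diagnosis under section 5.0 and invisible to the query. The same holds for a patient recorded only as suspected disease.

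This matters because recruitment is itself an outcome. Section 1.0 names it among the feasibility aims that are to inform the randomised trial. The query is the one route in which the team works from a list, so it directly generates counts of people approached and screened. If that list covers one of three admitted diagnoses, the counts from it describe a different pool from the one that the criteria define. As planned, the data would not show how far the two pools differ, because neither qualifying diagnosis nor route is recorded for people who are approached but not enrolled.

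**Working it through.** The plan states no recruitment rate or target proportion and makes no sample size calculation, so there is no figure to reproduce. The check is a comparison of the texts, followed by an illustration of how much the mismatch could matter.

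**Step 1: diagnosis by diagnosis**

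| Qualifying record (section 5.0) | Eligible on diagnosis? | Can the query in section 8.0 list it? |
|---|---|---|
| Alzheimer's disease code | Yes | Yes |
| Suspected disease only | Yes | No |
| MCI only | Yes | No |

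The query also carries no severity limit. It can therefore list Alzheimer's disease patients with a FAST score above 4, who then fail screening. Percent eligible from this channel thus reflects Alzheimer's-coded patients of any severity, without the other two groups.

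**Step 2: the other routes.** Five of the seven state no diagnosis restriction: clinic referral, contacts from earlier studies, flyers, electronic and community advertising, and respite centres with early memory loss programmes. People with MCI or suspected disease can enter through these. The gap lies in one channel, not in the study as a whole.

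**Step 3: possible effect on the agreement proportion.** Holding the number of approaches fixed:

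shift = q × w × d

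- q: share of all approaches made through the query. Assumed 25% to 75%.
- w: share of the eligible population with MCI or suspected disease and no Alzheimer's code. Assumed 20% to 60%.
- d: difference in agreement between that group and the Alzheimer's-coded group. Assumed 0 to 20 points, in either direction.

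None of the three is in the documents. Results:

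- d = 0: the shift is 0, whatever q and w are.
- Low: 0.25 × 0.20 × 0.10 = 0.005, or 0.5 points.
- Middle: 0.50 × 0.40 × 0.10 = 0.02, or 2 points.
- High: 0.75 × 0.60 × 0.20 = 0.09, or 9 points.
- Bound if every approach were to an Alzheimer's-coded patient: 1 × 0.60 × 0.20 = 0.12, or 12 points.

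**Step 4: scale.** Exact (Clopper-Pearson) 95% intervals, taking the dyad as the unit and supposing that the ceiling of 30 is reached:

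| Approached | Agreeing | Proportion | 95% interval | Half-width |
|---|---|---|---|---|
| 60 | 30 | 50% | 36.8% to 63.2% | about 13 points |
| 100 | 30 | 30% | 21.2% to 40.0% | about 9 points |
| 300 | 30 | 10% | 6.8% to 14.0% | about 4 points |

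With 100 approached, the high case (9 points) is about as large as the half-width and the middle case (2 points) is well inside it. With 300 approached, the middle case is about half the half-width.

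**The case against.** The strongest reply is that nothing in the estimate is wrong. Agreement is defined among those approached. A patient whom the query never lists is in neither the numerator nor the denominator, and most routes are open to every diagnosis. This stands. A reader might infer that the narrow query skews the recruitment estimate, but the documents do not support that. A shift needs both a difference in agreement by diagnosis and a material contribution from the query, and neither is given.

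A second reply is that a list centred on Alzheimer's disease is a reasonable choice. The aim in section 1.0 speaks of people living with Alzheimer's disease, and the knowledge and quality-of-life scales are specific to it. The parenthesis may also be shorthand, since the data request itself is not in the documents. This stands in part. It could be a reason for a narrower query, but the protocol does not give it, and section 8.0 presents the report as matching the eligibility criteria.

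A third reply is that diagnosis is already collected at baseline (Table 2), so enrolled participants can be tabulated by it. That is correct, but it does not cover people approached or screened out.

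Three further inferences are tempting and should not be drawn:

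- That the query misses some particular fraction of eligible patients. The documents give no diagnosis mix, so any such figure only returns the assumption put in.
- That accrual has no slack. The statement that "we anticipate recruiting 1-2 dyads weekly during the recruitment period for up to 30 PWD/CG dyads" is given as a way to keep the team's workload even. It is a pacing figure that no choice of codes alters, and 30 is a ceiling.
- That the background singles out the mildest stage. Section 2.0 favours planning before severe impairment and lists diagnosis as one of several triggers. It does not name MCI.

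**Conclusion.** The mismatch is established from the text alone: the query covers one of the three diagnoses that section 5.0 admits, and no reason is given. The supportable consequence is limited. This channel under-represents MCI and suspected disease, so recruitment and percent-eligible figures that draw on it may not generalise to the full eligible population, and the planned screening data would not show by how much.

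No bias in the agreement proportion is shown, in size or direction. The illustrative range of 0 to about 9 points rests wholly on the assumed values of q, w and d. The conclusion also assumes that the query is run as worded and that a MCI or suspected-disease record does not usually carry an Alzheimer's disease code as well; if such codes often coexist, the gap is smaller. The point is modest but worth correcting, because recruitment figures are among the main products of a feasibility study.

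**What to change.** 1. In section 8.0, extend the honest-broker request to the ICD codes for MCI and for the suspected or unspecified diagnoses that the clinics use, so that it matches section 5.0. Alternatively, keep the narrower query and state why.
2. Confirm the FAST score at screening, as the eligibility criteria already require.
3. In section 12.0, add qualifying diagnosis and recruitment channel to the screening log. In the Statistical Analysis Plan paragraph, report approached, eligible and consented counts by both. For flyers and online posts, the first countable contact is the person who gets in touch.

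The cost is a revised data request, a line or two of protocol text and two log fields. The wider code list will bring some extra screen failures. Counts by diagnosis and channel will be small and should be read as description only.

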9.0 Consent Process

Electronic consenting-e-Consenting will be performed with eligible PWD/CG dyads that desire to participate in the study. Dyads identified through the recruitment process that are unavailable for face-to-face consenting will have spoken to the researchers by telephone to discuss the study and its demands as well as had any initial questions answered. Dyads will be asked to provide an email address to facilitate receipt of a REDCap survey link containing a scanned image of the most recently approved Informed Consent document (developed using the MUSC REDCap e-consent template). Dyads will be allowed as much time as necessary to read the consent document together in their own home or at a place/time of their choosing. They will be provided with contact information (telephone and email) for the researchers in the survey instruction header should they have additional questions prior to consenting to participation by adding their respective signatures to the form and submitting. Prior to providing physical e-consent researchers will coordinate with the dyads to ensure the availability of the researcher by telephone to answer any questions that may arise during the e-consent process. Once the e-consent is submitted a REDCap trigger will immediately notify the researchers, who will then countersign the document.

[figure not shown]
PWD with legal healthcare power of attorney: Caregivers that have a legal healthcare power of attorney for the PWD will provide consent for the PWD in addition to consenting for their participation as a caregiver.

PWD without legal healthcare power of attorney: PWD without legal healthcare power of attorney will be screened using the Evaluation to sign Consent (ESC) measures following review of the consent form. The ESC includes five items which determines the ability of a subject with cognitive impairment to sign consent using the following four questions; 1) name at least 2 potential risks incurred as a result of participating in the study 2) name at least 2 things that will be expected of him or her in terms of patient cooperation during the study, 3) explain what he or she would do if he or she no longer wished to participate in the study, 4) explain what he or she would do if he or she was experiencing distress or discomfort. Question 5 of the ESC was omitted as it relates to randomization which is not planned for this study. Subjects with dementia that correctly answer all four questions will complete an informed consent form. Ongoing consent will be assessed at the beginning of study visit 1 and 2 as well as during post intervention interviews. Caregivers will be instructed to notify the PI of any change in cognitive status of the PWD immediately. For any PWD with changes in cognitive status will be reevaluated with the ESC measures and reconsented.

10.0 Study Design / Methods

Intervention activities include delivering the intervention materials with up to 30 PWD/CG dyads with measurement of feasibility, process, and outcomes. Thirty enrolled PWD/CG dyads will be provided with the SUPPORT-D written materials, an electronic pdf of the SUPPORT-D booklet and links to electronic videos reviewing the content of the written booklet. Participants will be provided the option to utilize their personal mobile device to access digital content and MS Teams to determine which is method is preferred (print or digital) and to facilitate sharing of intervention materials with family members at a distance unable to review print materials. For those that do not have access to a personal mobile device a mobile device (tablet) with the digital content preloaded and MS Teams preloaded for use throughout the study period. Following consent and study enrollment, baseline measures will be completed electronically by participants via an email link or verbally by the PI or research assistant (RA). This is followed by an orientation visit with the PI or RA where participants will receive intervention materials, orientation for accessing digital material, instructions for sharing digital resources with friends and family and detailed instructions on how to access the video conferencing software MS Teams from the personal device/provided tablet for study visits and a support number to call for technical assistance if necessary. Participants will retain the device and printed materials for the length of the study. Participants will be asked to return provided tablet devices at the end of the 8-week study period. However, participants will retain printed materials and identical digital materials at the end of the study period. The first virtual study visit via telehealth (e.g., MS Teams) with the nurse interventionist will be scheduled within 1 week of receiving tablet device/orientation. During this first virtual study visit the SUPPORT-D intervention will be delivered via MS-Teams for approximately 60 minutes by the nurse interventionist using a manual for guidance and recorded for fidelity monitoring. To ensure standardized content is provided the nurse interventionist will respond to questions by referencing the provided materials. If questions go beyond content, the interventionist will advise patients to consult their provider and assist the PWD/CG dyad in crafting questions that address additional concerns. The focus of this visit will be to provide an overview of the intervention, review detailed content for the first two parts of the intervention (understanding the disease and caring for myself) and provide participants instruction in maintaining an electronic or paper self-report log of home use of SUPPORT-D materials including when, what and how (format), content was reviewed and if shared with others (who, when, feasibility). Dyads will be encouraged to review these materials at home and share information with other family members. The PI will conduct fidelity monitoring for 10% of all study visits. Two weeks after the first virtual study visit dyads will be scheduled for a second virtual study visit via with nurse interventionist for delivery of parts 3 and 4 (information for the caregiver and planning for the future) of the intervention via MS Teams and recorded for fidelity monitoring. This session should last approximately 60 minutes. The nurse interventionist will utilize a manual for guidance to tailor study visit discussions according to baseline data collection, emphasizing areas of evident knowledge deficit based on questionnaire responses. All participants will

Figure 2. Intervention Delivery Timeline

attend a virtual post-intervention meeting (study week 8) with the PI via MS-Teams during which post-intervention data will be collected and a time scheduled for returning the tablet device. The PI will meet with the nurse interventionist weekly during the intervention. Each dyad will receive the SUPPORT-D intervention for a span of six-weeks with a two-week post intervention follow up (8-week total study period). The timeline for intervention delivery is also described in Table 2.

Post-intervention interviews. At the conclusion of the study period all dyads (30 dyads) will be asked their willingness to participate in post-intervention key informant interviews. Of those that express a desire to participate 10 dyads will be randomly selected via computer to participate in a post intervention interview with the PI to obtain more in-depth feasibility data related to accessibility, usability, and adherence to the intervention. A qualitative descriptive approach will be used to conduct the semi-structured interviews, which will last 45-60 minutes. An interview guide with open-ended questions and probes will be used to guide the semi-structured interview. Interviews will be recorded for the purposes of transcription for data analysis.

Table 2: Variables for Aims 1 and 2

McMillan Good Death Model Domain and major tasks	Measure/Instrument/ Psychometrics/Instrument scoring	Data sources and time points
Fixed characteristics of the patient		
Demographics/clinical characteristics	Age, gender, race, education, health history, date of diagnosis, diagnosis, # comorbidities	PWD/ CG, baseline
Modifiable dimensions of patient experience		
Knowledge	Alzheimer's Disease Knowledge Scale (ADKS), 30-items (TF), Cronbach's alpha .80 ²³ , summed total of correct items	PWD/CG, baseline and post-intervention
Acceptability of Intervention	Acceptability of Intervention Measure (AIM), 4 items; Cronbach's alpha 0.75-0.90 ²⁴ , calculated mean	PWD/CG, post-intervention
Feasibility	# days intervention use recorded, # times intervention materials shared, rates of recruitment, % eligible, consented, # times unable to access digital materials or meeting software; Intervention Appropriateness Measure (IAM) 8 items; Cronbach's alpha (0.77-0.87) ²⁴ , calculated mean Feasibility of Intervention Measure (FIM) (0.79-0.94) ²⁴ , calculated mean, content analysis from key informant and post-intervention interviews	PWD/CG, baseline, study visits 1 and 2, post intervention
Caregiver Burden	Zarit Caregiver Burden, 12 items; Cronbach's alpha 0.88 ²⁵ , summed score across items	Caregiver, baseline, post intervention
Perceived Stress Scale	Perceived Stress Scale (PSS); 10 items Cronbach's alpha > .70 ²⁶ , summed score across all items	PWD/CG, baseline, and post-intervention
Symptom Burden	Promis-29 v. 2.1, 29 items; Cronbach's alpha 0.89-0.95 ²⁷ , summed score converted to T-score ²⁸ Physical function, anxiety, depression, fatigue, sleep, quality, satisfaction with social role, and pain	CG/PWD (if able), baseline and post-intervention
Quality of Life	Quality of life-Alzheimer's Disease (QOL-AD); 13 items; Cronbach's alpha 0.74 for patients 0.66 for proxies ²⁹ , summed score	PWD (if able)/CG proxy, baseline, and post-intervention
Disease Preparedness	Self-Efficacy for Caregiving; 8 items; Cronbach's alpha 0.88, test-retest reliability .79, mean score across items Carer Support Needs Assessment Tool, 14 items summed score ³⁰	CG, baseline, and post-intervention
Safety	Safety Assessment Scale, 32 items, ICC 0.91, test-retest reliability 0.88 ³¹ , summed score across items	CG, baseline, post-intervention
Technology literacy	Digital Health Literacy Instrument; 21 items, Cronbach's alpha 0.87 ³² , total mean score	PWD/CG baseline and post-intervention
Care-system interventions		
Advance Care Planning (ACP)	ACP Survey, 2 items (Y/N) Pt completed >50% ACP-Y/N	PWD/CG, post-intervention

Additionally, those that complete the study will be invited to participate in a semi-structured interview to provide additional feedback on the digital version of the SUPPORT-D intervention. The same process described for the post-intervention interviews will be used to gather this feedback.

Measures. Self-report and proxy assessments will be completed by PWD, and CG utilizing participant personal mobile device or provided tablet to electronically answer the study measures directly into REDCap or asked verbally by the PI or PC. Measures of knowledge, acceptability, feasibility, stress, symptom burden, quality of life, disease preparedness, safety, technology literacy and advanced care planning will be collected from PWD/CG dyads. Specific instruments, scoring and psychometric properties are described within Table 2. The PI or PC will be present during baseline and post-intervention data collection to answer questions but will be unobtrusive during data collection. The data will be stored in REDCap.

Statistical Analysis Plan: We will obtain multiple measures to assess feasibility and inform future efficacy and effectiveness trials. Variables pertaining to the study procedures and participant demographic variables will also be collected. Data to be collected is described within Table 2. Specifically, 95% confidence intervals for proportions will be used to estimate dichotomous outcomes including proportion of participants who agree to participate out of those approached, and the proportion adherent to the intervention protocol (i.e., attendance at all study visits). Frequency distributions, median and mean responses (with 95% confidence intervals) will be obtained for continuous feasibility measures (e.g., time spent using SUPPORT materials between study visits, number of times SUPPORT content shared with others) as well as measure of practicability (e.g., number of calls for assistance, inability to access telehealth meeting software, number of chat messages received for intervention content related questions). Qualitative data gathered from post-intervention key informant interviews will be analyzed using directed content analysis.³⁴

Outcome measures and estimates of preliminary impacts: Measures of central tendency (mean, median), variability and frequency distributions as appropriate will be used to analyze demographic and clinical characteristics. Variability estimates of changes from baseline to post intervention for knowledge, quality of life, symptom burden, stress, and safety with 95% confidence intervals (without p-values) will be provided.

Sample size considerations: The purpose of this study is to establish feasibility, acceptability, and practicability of implementing the SUPPORT-D intervention, therefore a sample size calculation was not performed. Sample size for Phase II was determined for pragmatic reasons including time to deliver intervention, and availability of mobile devices for intervention delivery, The PI and PC plan to recruit participants over a three-month period using methods described within section 8 of this protocol. To ensure a consistent workload of the PI and interventionist we anticipate recruiting 1-2 dyads weekly during the recruitment period for up to 30 PWD/CG dyads.

Compensation: Reimbursement for dyads will be \$100 provided in \$25 increments over four time periods (enrollment/baseline data collection, study visit 1, study visit 2, and post intervention visit) with dyads in key informant interviews receiving an additional \$25.

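### The home-use log is introduced up to 7 days after participants receive the materials, and the end of the use window is left undefined

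*Combined protocol and SAP*

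**What the plan says.** Section 10.0 sets out the sequence. After consent and baseline measures, the next contact is described as: "orientation visit with the PI or RA where participants will receive intervention materials, orientation for accessing digital material, instructions for sharing digital resources". The first virtual study visit is to be "scheduled within 1 week of receiving tablet device/orientation". Among the stated purposes of that first visit is to "provide participants instruction in maintaining an electronic or paper self-report log of home use of SUPPORT-D materials". No earlier contact is described as introducing the log, and no date is given on which logging stops.

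The second session is fixed relative to the first: "Two weeks after the first virtual study visit dyads will be scheduled for a second virtual study visit". Parts 3 and 4 of the programme are taught there. The intervention spans six weeks, and a post-intervention meeting follows in study week 8.

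For analysis, the Statistical Analysis Plan in section 10.0 gives as one example of a continuous feasibility measure "time spent using SUPPORT materials between study visits", without naming the visits. Its companion example, a count of sharing with others, has no window. The Feasibility row of Table 2 lists "days intervention use recorded, # times intervention materials shared" among several variables, and its time points are baseline, the two numbered visits and post-intervention.

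**The concern.** Use of the intervention is named in the study's aim (section 1.0). Making it easier to share content with distant relatives is one stated reason for the digital format (section 10.0). Both are meant to inform a later randomised trial, so the period over which they are counted should match the period in which they can occur.

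As written, access begins at orientation but recording begins at visit 1. Anything read, watched or passed on in between has no described route into the data, and it may not be reliably recovered later. The length of this gap depends on when visit 1 is scheduled, so it differs between dyads for reasons unrelated to their use of the programme. The SAP plans means, medians and 95% confidence intervals for such measures, with no stated adjustment for days observed.

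At the other end, two analysts could follow the plan faithfully and report different exposure, because the visits that bound the use-time measure are not named. This matters most for Parts 3 and 4, which hold 4 of the 7 topics in Table 1 and are taught only at visit 2.

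**Working it through.** The plan states no figure for the length of the use window, so there is none to reproduce. The check is timeline arithmetic from the plan's own intervals.

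**Inputs (section 10.0)**
- Materials received: orientation visit, taken as day 0. This is an assumption; the documents do not say what starts the eight-week clock.
- Visit 1: day 0 to 7. Log instruction is given here.
- Visit 2: visit 1 + 14 days, so day 14 to 21.
- End of intervention: 6 × 7 = day 42.
- Post-intervention meeting: 8 × 7 = day 56.

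**Start of the window**
- Days of access before log instruction: 0 to 7.
- Largest share of the intervention: 7/42 = 16.7%.
- Largest share of the study: 7/56 = 12.5%.
- If the clock starts at visit 1 instead, a 7-day lag lies in front of it. The largest shares of access time are then 7/(42 + 7) = 14.3% and 7/(56 + 7) = 11.1%.

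**Comparability between dyads**
- With orientation as day 0 and logging to day 56, the logged period is 56 − 0 = 56 days for a dyad with no lag and 56 − 7 = 49 days for a dyad with the full lag.
- At the same daily rate of use, the second dyad's count would be 49/56 = 87.5% of the first's, from scheduling alone.
- If the clock starts at visit 1, both dyads log 56 days. What then varies is the unlogged access in front, 0 to 7 days.

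**End of the window: two readings of the SAP example**
- *Narrow (visit 1 to visit 2):* 14 days, which is 14/42 = 33.3% of the intervention or 14/56 = 25.0% of the study. Days left out after visit 2: 42 − 21 = 21 to 42 − 14 = 28 of the intervention (50.0% to 66.7%), or 56 − 21 = 35 to 56 − 14 = 42 of the study (62.5% to 75.0%). All use of Parts 3 and 4 after they are taught would fall outside.
- *Wide (to the post-intervention visit):* 49 to 56 of 56 days (87.5% to 100%). Use of Parts 3 and 4 after visit 2 is included.

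**Which reading the text supports**
- For the narrow one: the numbered study visits are only 1 and 2, and both Table 2 and the Compensation paragraph list the last contact separately.
- For the wide one: the Compensation paragraph also calls that last contact a visit, Table 2 gives the Feasibility row a post-intervention time point, and nothing says logging stops at visit 2.
- Table 2 does not settle the matter, because its time points belong to a row that mixes several variables.

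**Whether anything else covers the start gap**
- At baseline no materials have been issued, and at visit 1 the log is only being introduced, so neither Table 2 time point can supply log data for the gap.
- Section 13.0 provides for weekly contact and log review, for adverse events, progress, compliance and fidelity. It does not describe collecting earlier use retrospectively.

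**The case against.** A reader might infer that exposure is truncated at both ends, and that use of Parts 3 and 4 after their session is left out. The documents do not support that. The inter-visit wording is one example, attached only to time spent, and the visits are unnamed. The counts of days used and times shared carry no window. Table 2 lists a post-intervention collection point for the row that holds them, section 13.0 does not limit log review to the period before visit 2, and no passage ends logging there. This part of the objection stands in full: the end of the window is undefined, not shown to be short.

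The start gap can also be played down. Seven days is a maximum, and some dyads may have visit 1 almost at once. Nothing forbids a participant from entering earlier use retrospectively. Nor do the documents show that use is heaviest in the first days, so no such claim is made here. The percentages depend on where the clock starts. The timeline figure (Figure 2) is not reproduced in the text available, and it might bear on timing. These points limit the size of the gap and the certainty about it. They do not supply a capture method for the interval, because retrospective entry is permitted only by silence.

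Finally, this is a feasibility study with no p-values and no sample size calculation, and interviews with 10 dyads will explore usability and adherence. That is a fair reason to keep the point modest. But the interviews cover a subset and are not described as a count of use or sharing, which the SAP proposes to estimate with confidence intervals.

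**Conclusion.** The start gap holds. Following the plan as written leaves 0 to 7 days of access per dyad with no described recording of use or sharing. That is at most 16.7% of the intervention span or 12.5% of the study if orientation is day 0, and 14.3% or 11.1% of access time if the clock starts at visit 1. The gap varies with scheduling.

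The end of the window is ambiguous. Readings from 14 days up to 56 days are compatible with the text, and only the narrow one would omit use of Parts 3 and 4 after they are taught. Section 10.0, Table 2 and the SAP need to be reconciled on this. The conclusion assumes that the log is not introduced anywhere other than where section 10.0 describes it. The change is worth making because it improves capture of a core feasibility measure at almost no cost.

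**What to change.** 1. In section 10.0, move the log and its instruction from study visit 1 to the existing orientation visit, so that logging starts on the day the materials are received.
2. State that logging runs to the post-intervention visit, and say what starts the eight-week clock.
3. In the SAP, name the visits that bound the use-time measure. Summarise use and sharing for three intervals (orientation to visit 1, visit 1 to visit 2, visit 2 to post-intervention) and in total, each divided by that dyad's days of observation.
4. Align the Feasibility row of Table 2 by stating which time points apply to days of use and times shared.

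The cost is a change of wording, a few minutes moved between two existing contacts, and up to one extra week of log-keeping for participants. No new visit or instrument is needed.
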